1.2 SAP Approval and Revision

The SAP will be reviewed and approved by the ACTIV 4 Host Tissue stakeholders listed below prior to the first interim analysis for any arm:

- ACTIV 4 Host Tissue Study Chair: [name]
- ACTIV 4 Host Tissue DCC PI: [name]
- NHLBI Statistician: [name]

Amendments to the SAP must also be approved by the stakeholders listed above. Amendments must be version controlled and numbered. All revisions will be summarized briefly, including the changes made, new version number, and the author of the changes.

2 STUDY DESIGN

2.1 Summary

The ACTIV 4 Host Tissue master protocol describes a common approach to studies of blinded, placebo-controlled therapeutic approaches of host-tissue targeted therapies in hospitalized COVID-19 patients. The Master Protocol is designed to be flexible in the number of study arms, to have a common placebo group, and to allow for stopping and adding of new therapies, while using a common approach to design, analysis, and implementation.

2.2 Study Arms and Pooled Placebo

The ACTIV 4 Host Tissue platform consists of multiple study arms that represent distinct drug therapies. During the randomization process, each participant is assigned a study arm and either the active drug or a matching placebo. The statistical analyses described herein will be implemented separately for each study arm. However, placebo participants will be pooled across arms. For each study arm, the placebo comparator group will consist of all placebo participants that were *eligible* for that study arm at the time of randomization. A participant is considered eligible for a study arm if assignment to that arm was a possible outcome of randomization. Participants that decline to participate in any one or more study arms prior to

randomization will be treated as ineligible for those arms. The randomization process is designed to ensure balance in each active drug group versus the corresponding placebo comparator group.

2.3 Randomization

Participants are randomized individually at enrollment using a central electronic system. The permuted block method, with stratification by study site and study arm eligibility is used to generate treatment assignments. An eligibility stratum is the collection of study arms for which a participant is eligible. Stratification by site ensures balance across the active and pooled placebo comparator groups at regular enrollment intervals at each site, thus mitigating the impact of site heterogeneity on assessments of treatment effect. Each block contains a multiple of $m(m+1)$ assignments, where m is the number of study arms in the corresponding eligibility stratum. Within each block there are an equal number of allocations across study arms and, for each study arm, there are m active and 1 placebo assignments. For example, in the TXA127 and TRV027 eligibility stratum, each block consists of the following allocations, or multiples thereof:

Study Arm	Placebo/Active
TXA127	Active
TXA127	Active
TXA127	Placebo
TRV027	Active
TRV027	Active
TRV027	Placebo

Thus, within each block, assignments are balanced across study arms, and the active assignments are balanced with the pooled placebo assignments. The block size multiple is either 1 or 2, selected uniformly at random for each block.

2.4 Blinding

For organizational purposes, the randomized assignment comprises two distinct pieces of information: 1) study arm, and 2) active vs. placebo assignment. The study arm is not blinded, whereas the active/placebo assignment is blinded from participants and investigators (other than unblinded personnel as required for study operations, data quality/analysis, and safety). Blinding will remain in place until all participants have completed the study, all data quality monitoring is complete, and the database is locked.

3 OUTCOMES

3.1 Primary Outcome

The primary outcome for the ACTIV 4 Host Tissue platform is oxygen free days (OFD) at day 28. OFD will be calculated as the number of calendar days during the first 28 days after randomization during which the patient was alive and not receiving supplemental oxygen therapy. Participants who chronically used supplemental oxygen prior to their COVID-19 illness will be considered oxygen free when their use of supplemental oxygen does not exceed the level of oxygen support (measured in daily L/min·h by nasal cannula) used prior to COVID-19 illness. Supplemental oxygen therapy includes the following: supplemental oxygen by nasal cannula, supplemental oxygen by face mask, high flow nasal cannula (HFNC), non-invasive ventilation (NIV), invasive mechanical ventilation (IMV), or extracorporeal membrane

oxygenation (ECMO). The day of randomization is defined as day 0. Starting with study day 1 (the day after randomization) and continuing for 28 days, study personnel will document whether the participant received supplemental oxygen therapy on each day for any duration of time. Use of supplemental oxygen at home after discharge will be assessed via telephone follow-up calls to the participant or surrogates. OFD will be calculated as 28 minus the number of days between and including the first and last days of supplemental oxygen use during the first 28 days after randomization. OFD will be coded as -1 for patients who died on or before study day 28. Hence, OFD may take any integer value between -1 and 28. OFD is an ordered categorical (i.e., ordinal) outcome that may be interpreted as a count of days. Additional details about calculating OFDs may be found in the SAP appendix (see Appendix: Algorithm to Compute Primary Outcome).

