OFD will be calculated as the number of calendar days during the first 28 days after randomization during which the patient was alive and not receiving new supplemental oxygen therapy. Patients will be considered to be receiving supplemental oxygen therapy when they are receiving any of the following: supplemental oxygen by nasal cannula, supplemental oxygen by face mask, high flow nasal cannula (HFNC), non-invasive ventilation (NIV), invasive mechanical ventilation (IMV), or extracorporeal membrane oxygenation (ECMO). The day of randomization is denoted as Day 0. Starting with calendar day 1 (the day after randomization) and continuing for 28 days, study personnel will document whether the patient received oxygen therapy on each day for any duration of time. While the patient is in the hospital, the highest level of respiratory support received during each calendar day will be documented according to the 8-category WHO COVID-19 clinical status scale. Categories 4, 5, 6, and 7 indicate in-hospital oxygen use.

Use of supplemental oxygen at home after discharge will be assessed via telephone follow-up calls and text/email responses to the participant or surrogates. Patients who chronically used supplemental oxygen prior to their COVID-19 illness will be considered oxygen free when they return to the same level of oxygen support, they had been using prior to COVID-19 illness. For example, a patient who chronically used supplemental oxygen at 4 liters per minute via nasal cannula before COVID-19 and who was intubated for acute management of COVID-19 would be considered oxygen free for calculation of the primary outcome when he/she returned to oxygen support via nasal cannula at 4 liters per minute or less.

The primary outcome, OFD, will be calculated as 28 minus the number of days with oxygen use during the first 28 days after randomization. OFD will be coded as -1 for patients who died before study day 28. Hence, the range for OFD is from -1 to 28 days. The first day of follow-up is the day after randomization, so 28 OFDs are the maximum possible days (Appendix A: Primary study outcomes).

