10 APPENDIX: ALGORITHM TO COMPUTE PRIMARY OUTCOME

The primary outcome is oxygen-free days at study day 28. It can take values -1, 0, 2, ..., 27, 28. When computing oxygen free days, the “outcome” for each participant should be a length 30 vector of zeros and ones that indicate which of the 30 possible values (-1, 0, 2, ..., 27, 28) that OFDs could take for that participant. This representation allows for arbitrary censoring of the outcome. For example [0,1,1,0,0,...,0] indicates that OFDs could be either 0 or 1. If there is loss-to-follow-up, withdrawal, or missing follow-up information, there can be interval censoring. The algorithm below is designed to compute OFDs in this representation.

- If participant was deceased by study day 28, OFDs is [1,0,0,0,0,...,0]
- For study day 1 through 28, compute whether or not supplemental oxygen was used (code with “yes” or “no”), or if supplemental oxygen use was uncertain (code with “?”).
 - For our purposes supplemental oxygen means oxygen use that exceeds any pre-enrollment home oxygen use. Home oxygen use is recorded in the “Medical History” form in variables mhco2, mhio2, and the amount (L/m) in field home_ox. If a participant had not used pre-enrollment home oxygen, then it should be assumed that all hospital and post-discharge use of oxygen counts against oxygen-free days. If a participant had used pre-enrollment home oxygen, then only the supplemental oxygen use that exceeds the amount used at home should count against oxygen-free days. If the participant is in the inpatient phase of the study and using standard supplemental oxygen (o2type = “O2 by mask or nasal prongs”), then the L/m recorded on the vitals signs form (o2_lpm_cannula_sofa) must exceed the amount used at home (home_ox). If hospital oxygen use takes any other value except “No O2 therapy” and “O2 by mask or nasal prongs”, then that study day should count against oxygen free-days.
 - If the participant is in the outpatient phase of the study (i.e., after discharge from the enrollment admission or after 28 days, whichever comes first), but is not hospitalized, then only the post-discharge home oxygen use that exceeds the amount used at home prior to enrollment (if any) will count against oxygen-free days. The phone script and outpatient form are designed to record only the home oxygen use that exceeds any pre-hospitalization oxygen use.

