 - If the participant is in the outpatient phase of the study, but is hospitalized, the branching logic on the outpatient form determines whether the participant had used oxygen. Any hospital oxygen use during the outpatient phase counts against oxygen-free days.
 - If the preceding calculations cannot be made for any particular study day, then the supplemental oxygen status is “?” for that study day.
- The preceding step results in “yes”, “no”, or “?” for each study day 1 through 28.
 - If there are no “?” values, then OFDs is 28 minus the number of days between and including the days of the first “yes” and the last “yes”.
 - If there are “?” before the first “yes” or after the last yes, then OFDs is partially observed and multiple values are possible. To compute the possible values, consider each possible pair of first ‘yes’ and last ‘yes’ days, and compute the associated OFDs.

OFDs should be represented as a vector of length 30, one element for each value that OFDs can take: -1, 0, 1, ..., 27, 28. There should be a 1 for each element that OFD that is possible for this participant, and a zero otherwise. The -1 (first) element should take a value 0 if the participant was known to be alive at day 28 and 1 otherwise.

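### SAP 3.1 judges chronic oxygen users in daily L/min·h but the scoring algorithm and protocol use L/min, and the algorithm's readmission rule gives no home-level allowance

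*SAP*

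**What the plan says.** SAP 3.1 treats a chronic user as oxygen free when supplemental use does not exceed the "level of oxygen support (measured in daily L/min·h by nasal cannula) used prior to COVID-19 illness". It then refers the reader to the SAP appendix for details of the calculation.

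SAP Appendix 10 takes pre-enrollment home use from the medical history form, "and the amount (L/m) in field home_ox". For an inpatient day on mask or nasal prongs to count as oxygen use, "then the L/m recorded on the vitals signs form (o2_lpm_cannula_sofa) must exceed the amount used at home (home_ox"). Inpatient days on any higher level of support count regardless. For days at home after discharge the appendix says: "The phone script and outpatient form are designed to record only the home oxygen use that exceeds any pre-hospitalization oxygen use". It gives no unit there. For a participant who is back in hospital during the outpatient phase, it says: "Any hospital oxygen use during the outpatient phase counts against oxygen-free days".

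Protocol 5.3.1, repeated in Protocol 19.2, gives a worked example: a patient on 4 L/min before COVID-19 is oxygen free once he or she has "returned to oxygen support via nasal cannula at 4 liters per minute or less". Hours play no part.

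Daily status is turned into the score in SAP 3.1: "OFD will be calculated as 28 minus the number of days between and including the first and last days of supplemental oxygen use".

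**The concern.** The SAP gives two yardsticks for the same primary-outcome decision. One multiplies flow by hours; the other uses flow. The SAP does not say which of its two sections prevails. Protocol 8.1 gives the SAP precedence over the protocol's statistical section, but that cannot settle a conflict inside the SAP.

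The 3.1 yardstick also lacks data. Appendix 10 names a flow field for home use and a flow field for inpatient use, but no hours field for either. The home-oxygen fields mhco2 and mhio2 are named without definition and do not enter the comparison. SAP 3.1 itself describes a yes/no record: "study personnel will document whether the participant received supplemental oxygen therapy on each day for any duration of time".

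The readmission sentence is a second problem. SAP 3.1, Protocol 5.3.1 and Appendix 10's own opening definition all exempt oxygen at or below the pre-illness level. As written, the readmission sentence does not.

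At stake is whether two programmers working from the same SAP would derive the same primary outcome for chronic oxygen users, who are eligible under Protocol 6.1 (criterion 4).

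**Working it through.** **1. The scoring formula.** OFD = 28 − (last oxygen day − first oxygen day + 1), or 28 if there is no oxygen day. With consecutive oxygen days from day 1, this reproduces Protocol Table 4: 18 days gives 10, 3 gives 25, 27 gives 1, 28 gives 0, none gives 28. It also reproduces the SAP 6.2 example: oxygen on days 1 to 10, then loss to follow-up, gives at most 18.

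**2. The two tests.** Let home use be F L/min for H hours a day, and study-day use f L/min for h hours.
- SAP 3.1: oxygen day if f × h > F × H.
- Appendix 10, inpatient mask or nasal prongs: oxygen day if f > F.

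If h = H, the two are the same test. They can disagree only when daily hours change.

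**3. Illustrative records.** Flows and hours are assumptions. Each record treats the days that decide the score as inpatient days on mask or nasal prongs.

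| Home use | Study days | OFD, SAP 3.1 | OFD, Appendix 10 |
|---|---|---|---|
| 4 × 24 = 96 | 6 × 24 = 144 on days 1–7; 4 × 24 = 96 after | 28 − 7 = 21 | 28 − 7 = 21 |
| 2 × 16 = 32 | 4 × 24 = 96 on days 1–5; 2 × 24 = 48 on days 6–14; 2 × 16 = 32 after | 28 − 14 = 14 | 28 − 5 = 23 |
| 2 × 8 = 16 | 3 × 24 = 72 on days 1–7; 2 × 24 = 48 on days 8–28 | 28 − 28 = 0 | 28 − 7 = 21 |
| 2 × 8 = 16 | 2 × 24 = 48 on days 1–28 | 28 − 28 = 0 | 28 |
| 2 × 24 = 48 | 4 × 8 = 32 on days 1–28 | 28 | 28 − 28 = 0 |

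The continuous home user scores the same under both rules. The last two rows are extremes, and they show that the discrepancy can run in either direction.

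**4. Readmission.** Take a chronic user above the home level on days 1–5, at the home level after that, and readmitted on day 27 only, at the usual home flow.
- Readmission sentence as written: first day 1, last day 27, so OFD = 28 − 27 = 1.
- Home-level allowance applied: last day 5, so OFD = 28 − 5 = 23.

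One day at home-level oxygen costs 22 OFDs, because the first-to-last rule also counts the days in between.

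**5. Overall size.** The documents give no share of chronic users. Assuming 2% to 10% of 600 participants gives 12 to 60 people. If every one of them differed by 28 days in the same direction, the pooled mean OFD would move by 28 × 0.02 = 0.56 to 28 × 0.10 = 2.8 days. With a 9-day gap (14 versus 23) it would move by 9 × 0.02 = 0.18 to 9 × 0.10 = 0.90 days. Both are upper bounds, since continuous users do not contribute.

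**The case against.** The best defence is that only one version can be coded. If 3.1 cannot be computed from the named fields, the programmer will follow Appendix 10, which 3.1 itself cites and which agrees with the protocol example. On that view, one parenthesis in 3.1 is out of line. This is largely right and keeps the point small. It does not remove the need to correct the primary-outcome definition, or to name an hours variable if the parenthesis is meant.

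A reader might infer that a typical chronic user could score either 0 or 28. The documents do not support that. A score of 28 needs home-level flow from day 1, whereas a chronic user would ordinarily qualify through increased oxygen. Criterion 4 also accepts low saturation on room air, so the case is not excluded. However, the planning table in SAP 6.6 puts 0.000 at OFD 28.

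A reader might also infer that Appendix 10 uses flow throughout. Its explicit L/min test covers only inpatient days on mask or nasal prongs. The unit for days at home rests on a phone script that is not in the documents, so no conflict can be shown for those days.

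On readmissions, the sentence may be meant to inherit the appendix's general definition, or to be a deliberate exception, and the form's branching logic is not available. That is a fair reason to ask for clarification, but the literal text still conflicts with the definition above it. It also stands that no readmission flow field is named, so an above-home-level test may not always be computable.

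**Conclusion.** The unit conflict is real, and it sits in the primary outcome. It affects only chronic users whose daily hours of oxygen change. For them the gap may be moderate or large: 9 days in one illustrative record, 21 in another, 28 at the extreme. The readmission sentence is a separate conflict and can cost a chronic user 22 days for one day of home-level oxygen.

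The size for the trial as a whole is unknown, because the shares of chronic users, intermittent users and readmissions are not given. The effect on the trial's conclusion is probably small. A reader might infer bias toward one arm or an inflated type-I error. Nothing in the documents shows either: outcome assessors are blinded (Protocol 6.7 and 19.1), so the expected result is noise and a primary dataset that cannot be reproduced from the text. The reason to settle it before unblinding is that a choice of rule made afterwards would be post hoc.

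**What to change.** Make two edits to the SAP before unblinding.

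1. In SAP 3.1, state the comparison in L/min, matching Protocol 5.3.1, Protocol 19.2 and Appendix 10. If L/min·h is intended, name the variables that hold daily hours for home and study oxygen and change Appendix 10 to use them.
2. In Appendix 10, state that oxygen during a readmission counts only if it exceeds the home level. Where a chronic user's readmission flow is not recorded, code the day `?`. The algorithm already has this code and the likelihood already accepts it: in the readmission example, the possible OFD values would be 1 and 23.

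The first edit, in its L/min form, is wording only. The second is wording plus a condition in the derivation code, and it needs a check on whether readmission flow is captured. Keeping L/min·h would cost more, because hours data would have to exist.

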3.2 Secondary Outcomes

Listed below are the ACTIV 4 Host Tissue platform secondary outcomes. The “Test Order” field indicates the order in which key secondary outcomes will be tested, using the fixed-sequence method, to control the familywise type-I error probability across the primary and key secondary outcomes.

Description	Type	Test Order	Analysis Method
Alive and oxygen free at day 14	Binary		LogR
Alive and oxygen free at day 28	Binary		LogR
Alive and respiratory failure-free at day 14	Binary		LogR
Alive and respiratory failure-free at day 28	Binary	1	LogR
Alive and free of new IMV at day 14	Binary		LogR
Alive and free of new IMV at day 28	Binary		LogR
Mortality in-hospital	Binary		LogR
Mortality at day 28	Binary	3	LogR
Mortality at day 60	Binary		LogR
Mortality at day 90	Binary		LogR
WHO 8-point ordinal scale at day 14	Ordinal		POLR
WHO 8-point ordinal scale at day 28	Ordinal	2	POLR
WHO 8-point ordinal scale at day 60	Ordinal		POLR
Hospital-free days at day 28	Ordinal		POLR
Respiratory failure-free days at day 28	Ordinal		POLR
Ventilator-free days at day 28	Ordinal		POLR

LogR – Logistic Regression; POLR – Proportional Odds Logistic Regression

The WHO 8-point ordinal scale is defined as most severe clinical status among the following on the day of assessment:

1. Ambulatory – Not hospitalized, no limitation of activities
2. Ambulatory – Not hospitalized with limitation of activities or home oxygen therapy
3. Hospitalized Mild Disease – Hospitalized, no oxygen therapy
4. Hospitalized Mild Disease – Oxygen by mask or nasal prongs
5. Hospitalized Severe Disease – Non-invasive ventilation of high-flow oxygen
6. Hospitalized Severe Disease – IMV
7. Hospitalized Severe Disease – IMV + organ support with-vasopressors, RRT, or ECMO
8. Dead

Alive and respiratory failure-free at day 28, the WHO 8-point ordinal scale at day 28, and Mortality at day 28 are key secondary outcomes that will be treated as a family for testing

purposes, even though the studies will not be adequately powered to detect anything but a very strong treatment effect on these outcomes. A supplementary analysis to assess the evidence that treatment lowers the risk of death in a way that is consistent with its effect on nonfatal outcomes will be performed. A respiratory failure-free day is defined as a day alive without the use of HFNC, NIV, IMV, or ECMO.

3.3 Safety Outcomes

Safety outcomes include the following events, assessed daily during hospitalization or intermittently following hospital discharge. For each event, we will analyze two composite binary outcomes: 1) the occurrence of one or more such events by the end of study day 7 and 2) the occurrence of one or more such events by the end of study day 28.

Description	Type	Analysis Method
Hypotension	Binary	LogR
Allergic reaction, rash, or angioedema	Binary	LogR
Incident renal replacement therapy	Binary	LogR
Other PSESE	Binary	LogR

LogR – Logistic Regression

Hypotension is defined by low arterial blood pressure leading to either [1] initiation or increase in vasopressor therapy, [2] administration of a fluid bolus of 500 ml or more, or [3] modification of the dose or discontinuation of the study drug.

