	
Safety outcomes (systematically collected during index hospitalization):
 
 
• Hypotension as defined by low arterial blood pressure leading to either [1] initiation or increase in vasopressor therapy, [2] administration of a fluid bolus of 500 ml or more, or [3] modification of the dose or discontinuation of the study drug.
 
• Allergic reaction, including angioedema and rash
 
• Incident renal replacement therapy during hospitalization
 

Study Duration	Multiple arms can actively enroll concurrently for an anticipated 15 months.
Duration of Participant follow-up	Duration of hospitalization with post-discharge follow-up for up to 90 days after randomization. (Specific eligibility criteria are in the main protocol text)
Population	Patients hospitalized for COVID-19 with laboratory confirmed SARS-CoV-2 infection on oxygen therapy.
Study Sites	Sites affiliated with NHLBI-CONNECTS Network of Networks and other networks and sites with previous clinical trial experience. Selected sites will be sufficiently equipped and experienced to safely enroll and follow patients, and to produce accurate data. The number of enrolling sites will be informed by the number of hospitalized patients with COVID-19 at active sites, the sample size required, and projected patient accrual.
Planned Maximum Number of Subjects	
We expect the maximum sample size to be about 300 per interventional treatment arm.
 
Prior to the first interim analysis, sample size adequacy was re-assessed based on the pooled (across all active and placebo arms) distribution of the primary outcome. No adjustments to the maximum sample size were made. Placebo enrollment beyond 300 participants may be required to ensure there are sufficient concurrently randomized and eligibility-matched placebo participants for comparison with each active drug arm.

Description of Study Agents	Specific agents will be described within the agent-specific appendices. The therapies relevant to this Master Protocol must have some mechanistic link to preventing progression to critical illness, multiorgan failure, or death in patients with COVID-19 and related to the host tissue response to COVID-19.

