**PSESEs are exempt from adverse event reporting unless:**

1. the event is determined to be Serious and Definitely or Possibly Related to the study drug or study procedures;
2. the event is determined to be Unexpected and Definitely or Possibly Related to the study drug or study procedures; or

This approach is taken to avoid creating an overly cumbersome safety oversight environment by identifying expected clinical outcomes as safety events and obscuring real safety signals. Even as they are exempted from expedited reporting requirements, PSESEs will be reviewed regularly (unblinded, by treatment arm) by the DSMB to maintain the integrity of safety monitoring for the trial. PSESEs that meet none of the criteria above will not be recorded or reported as AEs.

PSESEs may occur during the initial hospitalization, lead to a re-admission, or occur in a later hospitalization during follow-up. The following are study-specific exempt serious events:

- Death (not Definitely or Possibly Related to the study drug or study procedures)
- Neurological Events:
  - Seizure

- Stroke
- Cardiovascular Events:
  - Hypotension as defined by low arterial blood pressure leading to either [1] initiation or increase in vasopressor therapy, [2] administration of a fluid bolus of 500 ml or more, or [3] modification of the dose or discontinuation of the study drug.
  - Atrial or ventricular arrhythmia
  - Cardiomyopathy
  - Cardiac arrest
  - Myocardial injury
  - Acute coronary syndrome
  - Hypertension as defined by elevated arterial blood pressure leading to either [1] initiation or increase in antihypertensive medications or [2] discontinuation of the study drug
- Respiratory events:
  - Hypoxemia requiring supplemental oxygen
  - Acute respiratory distress syndrome
  - Receipt of non-invasive or invasive mechanical ventilation
  - Receipt of extra-corporeal membrane oxygenation
- Gastrointestinal events:
  - Elevation in aspartate aminotransferase or alanine aminotransferase
  - Acute pancreatitis
- Renal events:
  - Acute kidney injury
  - Receipt of new renal replacement therapy
- Endocrine events:
  - Symptomatic hypoglycemia
- Hematologic or coagulation events:
  - Neutropenia, lymphopenia, anemia, or thrombocytopenia
  - Venous thromboembolism
- Dermatologic events:
  - Severe dermatologic reaction (e.g., Steven's Johnson Syndrome)

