## 22.5 Fostamatinib-specific safety considerations and potential medication interactions

Fostamatinib has a consistent safety profile, with the most common adverse reactions ( $\geq 5\%$  and more than placebo) being diarrhea, hypertension, nausea, respiratory infection, dizziness, ALT/AST increase, rash, abdominal pain, fatigue, chest pain and neutropenia. Warnings and precautions included in the US product label include hypertension, elevated liver function tests, diarrhea, neutropenia, and embryo-fetal toxicity.

- Fostamatinib must be discontinued in case the patient becomes pregnant.
- Concomitant use with strong CYP3A4 inhibitors with fostamatinib will increase exposure to the active metabolite R406 and may result in increased risk of adverse reactions. **Therefore, patients that cannot have strong CYP3A4 inhibitors held should be excluded from the Fostamatinib arm.** Strong CYP3A4 inhibitors that should exclude patients from the fostamatinib arm include: Atazanavir, Certinib, Clarithromycin, Cobicistat and cobicistat-containing coformulations, Idelalisib, Indinavir, Itraconazole, Ketocanazole, Levoketoconazole, Lonafarnib, Lopinavir, Mifepristone, Mibefradil, Nefazodone, Nelfinavir, Ombitasvir-paritaprevir-ritonavir plus dasabuvir, Posaconazole, Ribociclib, Ritonavir, Saquinavir, Telithromycin, Troleandomycin, Tucatinib, Voriconazole. Novel strong CYP3A4 inhibitors may be released after the writing of this protocol appendix. If you anticipate the patient will require a strong CYP3A4 inhibitor that is not included in the list above, please reference this regularly updated list: <https://drug-interactions.medicine.iu.edu/MainTable.aspx>

Fostamatinib itself is a weak CYP3A4 inhibitor and will result in a modest ( $\sim 1.25$  fold) increase in CYP3A4 substrates. Medications processed (activated or deactivated) by the CYP3A4 enzyme are here referred to as CYP3A4 substrate medications. Concomitant use of CYP3A4 substrate medications with Fostamatinib will modestly decrease the processing of the CYP3A4 substrate medication. If possible, CYP3A4 substrate medications should be held or have another medication substituted for them. Due to its modest effects, concomitant use of CYP3A4 substrate medications is not an exclusion criterion for this trial. However, investigators should carefully consider inclusion of patients taking CYP3A4 substrate medications with narrow therapeutic windows and should monitor closely for toxicities.

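### SAP 3.3 pools the remaining PSESEs into one undefined yes/no row, so fostamatinib's hypertension, transaminase and neutropenia signals get no effect estimate of their own

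*SAP*

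**What the plan says.** SAP 3.3 has four rows: hypotension; allergic reaction, rash or angioedema; incident renal replacement therapy; and Other PSESE. Each is binary and analysed by logistic regression, under the rule "we will analyze two composite binary outcomes: 1) the occurrence of one or more such events" by day 7, with a second version at day 28. The fourth row is not broken down.

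The components have to be read from Protocol 13.2. That list includes death not attributed to study drug or procedures, ARDS, non-invasive or invasive ventilation, and "Hypoxemia requiring supplemental oxygen". It also includes:

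- "Elevation in aspartate aminotransferase or alanine aminotransferase", with no multiple of the upper limit of normal
- "Neutropenia, lymphopenia, anemia, or thrombocytopenia", as one entry with no threshold
- "Hypertension as defined by elevated arterial blood pressure leading to either [1] initiation or increase in antihypertensive medications", or discontinuation of study drug

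Protocol 2 describes the population as "Patients hospitalized for COVID-19 with laboratory confirmed SARS-CoV-2 infection on oxygen therapy". Protocol 22.5 states: "Warnings and precautions included in the US product label include hypertension, elevated liver function tests, diarrhea, neutropenia, and embryo-fetal toxicity". Diarrhea is not on the PSESE list.

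**The concern.** A pooled yes/no outcome is useful when its components are of similar importance and are expected to move in the same direction. Here the row joins consequences of COVID-19, which the drug is meant to reduce, to toxicities that it may increase. The disease events are common, so they set the rate. The toxicities are diluted, and a benefit on the disease events pulls the odds ratio the other way.

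Whether the row is merely diluted or has no information at all depends on a rule that neither document states. Hypoxemia needing oxygen is the condition that brings patients into the trial, and the PSESE entry carries no qualifier such as new or worsened. Protocol 13.4.2 has a rule for conditions present at baseline, but it covers only clinical adverse events that are not PSESEs.

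At stake is whether the final fostamatinib analysis contains a prespecified effect estimate for the risks the label warns about, each of which also has its own subsection of dose-modification rules in Protocol 22.7.

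**Working it through.** The documents give no expected rate or precision for Other PSESE, so there is no stated figure to reproduce.

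**Inputs from the documents**
- Probability of 28 oxygen-free days: 0.000 in every column (SAP 6.6 table).
- 28-day mortality, pooled and blinded: 0.235 in the planning table from the first 100 participants, and 18.6% in the first 200 (SAP 6.6).
- Modelled mortality at an efficacy odds ratio of 1.65: 0.158 (same table).
- About 300 patients per group (SAP 6.6).

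**Assumptions**
- One toxicity occurs in 5% of placebo and 15% of active patients.
- It is independent of the other components.
- Day-28 mortality stands for the new-event background. This is approximate, because drug-related deaths are not PSESEs and the other PSESE types would add to it.

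**Reading A: oxygen continuing from entry counts.** A patient alive with no oxygen on days 1 to 28 has 28 oxygen-free days. The share with oxygen use or death is therefore 1 − 0.000 = 1.000 to the precision shown. With almost no event-free patients, the odds ratio is not estimable or carries no information.

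**Reading B: only new events count.** With background rate b and toxicity rate t, the composite rate is p = 1 − (1 − b)(1 − t).

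- Toxicity alone: OR = (0.15/0.85)/(0.05/0.95) = 3.35.
- b = 0.186: p = 1 − 0.814 × 0.95 = 0.2267 and 1 − 0.814 × 0.85 = 0.3081, so OR = 1.52.
- b = 0.235: p = 1 − 0.765 × 0.95 = 0.2732 and 1 − 0.765 × 0.85 = 0.3498, so OR = 1.43.
- b = 0.50: p = 0.525 and 0.575, so OR = 1.22.
- b = 0.95: p = 0.9525 and 0.9575, so OR = 1.12, with about 14 and 13 event-free patients per group.

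As a guide to precision, take the chance that a two-sided 5% comparison of two proportions excludes no difference: Φ[(|p1 − p0| − 1.96·SE0)/SE1], with SE0 from the pooled rate and SE1 from the separate rates. This is 98% for the toxicity alone, 62% at b = 0.186, 53% at b = 0.235, 23% at b = 0.50 and 5% at b = 0.95. For a smaller toxicity of 5% versus 10%, it is 64% alone, and 21% and 18% at the two mortality backgrounds.

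**Offset by benefit.** Suppose the drug also lowers mortality from 0.235 to 0.158, the effect the trial is sized to detect. The active composite rate is 1 − 0.842 × 0.85 = 0.2843 against 0.2732 on placebo, so OR = (0.2843/0.7157)/(0.2732/0.7268) = 1.06. A threefold odds ratio for toxicity would then appear as almost no difference.

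**Other routes to an estimate**
- Protocol 13.2 and 13.3: a PSESE also enters the adverse event data only if it is serious or unexpected and possibly or definitely related (13.3 adds uncertain relationship). Grade 3 or 4 severity brings in only events that are not PSESEs. Protocol 22.8 treats neutropenia, hypertension and most AST/ALT elevations as expected. Non-serious cases of these therefore generally stay in the PSESE data.
- Protocol 8.8 promises odds ratios for adverse events and other safety endpoints. Protocol 8.1 gives the SAP precedence, and the SAP names no model for these toxicities.

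**The case against.** Three arguments on the other side have weight.

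First, a reader might infer that the composite must be near 100% in both arms. The documents do not support that unconditionally. The 0.000 figure counts any oxygen use after randomization, including oxygen carried over from entry, and is not a PSESE rate. Sites could reasonably leave entry hypoxemia out, and the only floor that can then be derived is 18.6% to 23.5% mortality. Saturation remains one of two open readings.

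Second, a reader might infer that the plan hides the drug's toxicity. It does not. Under Protocol 13.2 the DSMB reviews PSESEs unblinded by arm, and SAP 7.2 has their frequencies reported to it. AST or ALT above five times the upper limit or baseline is an event of special interest with a narrative (Protocol 22.8 and 13.1). Diarrhea is outside the composite, and serious, related or grade 3 or 4 cases are recorded as adverse events (Protocol 13.3). All of this stands. It provides monitoring and counts, not a prespecified effect estimate for the final analysis.

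Third, SAP 3.3 introduces its rule with the words for each event, so the last row could mean each remaining PSESE type in turn. That is possible, and it makes the row ambiguous. It does not cure the problem, because the choice would be left until the data are in hand and the baseline rule would still be missing.

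**Conclusion.** The point holds as a specification gap with a real cost to interpretation. SAP 3.3 neither lists the components of Other PSESE nor says whether conditions present at randomization count. On its literal reading, the composite rate may lie anywhere from about 19% to essentially 100%. At the low end, an assumed toxicity with an odds ratio of 3.35 appears as about 1.4 to 1.5; at the high end the odds ratio is uninformative. A mortality benefit of the size planned for would bring the pooled value close to 1.

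The toxicity rates and independence are assumptions, and the background uses day-28 mortality only; no day-7 figure is given. SAP 5 excludes formal tests of safety outcomes, so the percentages above describe precision, not a decision rule. The primary efficacy analysis is not affected.

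**What to change.** In SAP 3.3, for the fostamatinib comparison:

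- Add named binary outcomes for hypertension (PSESE definition), AST/ALT elevation, neutropenia and diarrhea (from adverse event records), each with an odds ratio and 95% credible interval at days 7 and 28. State the laboratory thresholds used for analysis.
- Count only events new or worsened since randomization.
- Report the other PSESE types, including ARDS, as frequencies by arm. ARDS should not be dropped, since no efficacy outcome in SAP 3.1 or 3.2 covers it.
- Keep death, oxygen use and ventilation out of any pooled toxicity row. They are already analysed as efficacy outcomes.

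A model for every PSESE type is not advised: many would be sparse under flat-prior adjusted logistic regression.

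The cost is SAP wording and a few more models, some possibly sparse. Neutropenia must be extracted from the CBC data, because the PSESE entry groups it with other cytopenias. Diarrhea will reflect only cases that qualify for recording. Protocol 7.7.1 and Table 1 require daily CBC and liver tests only in the fostamatinib arm while the patient is in hospital on study drug. Pooled placebo patients assigned to another arm have them only as usual care, and the report should say so beside the laboratory outcomes.
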